### 3 Study design

#### 3.1 Primary, secondary and additional study designs

**Figure 1. Diagram of sample size by cohort and study arm**

- 3.1.1 **Primary study (PA1-2, SA3, SA5):** The primary study is a multi-site cluster RCT comparing GBC with GBC+PIPT for patients with acute LBP deemed to be high risk for transition to chronic LBP (RCT cohort). Data collection will be conducted at baseline, 6 months, and 12 months. Resource use, determined with EMR data, will be evaluated in a subset of patients.
- 3.1.2 **Secondary study (SA4-5):** A secondary ancillary prospective, observational cohort study will be conducted for those patients presenting with acute LBP

deemed to be low or medium risk. Patients with acute LBP who do not meet criteria for high risk will be identified for the prospective observational cohort. These patients will receive GBC and not be targeted with any specific study interventions, such as PIPT. Data collection will also occur at baseline, 6 months, and 12 months. The objective of this ancillary observational study is to precisely determine the rates of transition from acute to chronic LBP and resource use in the treatment of LBP.

## 3.2 Randomization

The study will be conducted in five distinct US geographical areas in each of which a minimum of 12 primary care clinics will be participating and enrolling patients. The unit of cluster randomization will be the primary care clinic site. Thus, in one geographical area, six PCP clinics will be randomized to the GBC arm and six to the GBC+PIPT arm. The unit of randomization and analysis is a cluster because the intention is to enhance the application of a stratified approach to treating LBP in primary care environments as a whole while minimizing contamination. When randomization at the individual level was considered, it was found to be impractical and susceptible to selection bias and contamination.

The randomization for each study site will be conducted by the study biostatistician and will be stratified by two factors: Total Back Pain Encounters (Factor 1) and % Medicaid/Self-Pay (Factor 2). First, the clinics will be ordered by Factor 1 and divided into subgroups (blocks). Clinics in each block will then be further ordered by Factor 2, and randomly assigned to either group A or group B, making sure that the two groups would be balanced in terms of both Factor 1 and Factor 2.

## 3.3 Primary, secondary, and additional study outcomes

3.3.1 **The first primary outcome of the study (PA1) is the presence or absence of chronic LBP.** This is determined through the patients' answers to a two-item Chronic LBP Questionnaire based on criteria developed by the NIH Task Force on research standards for chronic LBP. The questions are: 1) How long has low back pain interfered with your ability to do regular daily activities? 2) Think only about the past 6 months. How often has low back pain interfered with your ability to do regular daily activities? Chronic LBP is defined as a response of "more than three months" to question 1, and a response of "half the days or more than half the days" in the past 6 months to question 2.

3.3.2 **The second primary outcome of the study (PA2) is the Oswestry Disability Index.** Originally described by Fairbanks et al, the Oswestry LBP Questionnaire is a reliable, well-validated, easily-administered, disease-specific measure that results in an index of a patient's perceived level of function due to LBP and is based on ten areas of performance. Items include how the back pain impacts the patient's ability to care for themselves (washing, dressing, etc.), lift, walk, sit, stand, and sleep. It also assesses the effect of the pain on the patient's sex life (if applicable), social life, and ability to travel. Patient

stakeholders unanimously find this type of instrument more patient-centered than the standard pain numerical rating scale and believe that the Oswestry represents functional activities that can become impaired when they experience back issues and are important to them to overcome. Each area is scored from 0 - 5 with zero representing no limitation and five representing maximal limitation. The ten areas, which include an assessment of pain intensity, are added together, resulting in a maximum score of 50. This score is doubled and interpreted as a percentage of patient-perceived disability, with higher scores representing greater disability.

- 3.3.3 **A secondary outcome (SA3-5) is LBP-related medical resource utilization**, including 1) referrals to specialists (e.g., orthopedists, spine surgeons, physiatrists) and other health care providers, 2) tests (e.g., MRIs), surgical procedures (e.g., epidural steroid injections, laminectomy), and 3) prescription analgesics including opioids.

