- 9.1.13 **H5:** GBC+PIPT will have less transition to chronic LBP and will be more effective than GBC alone for improving functional outcomes and reducing LBP-related medical resource utilization for the subgroup of patients who are underserved or with depression. Because the interventions being studied do not specifically target obesity and smoking, and the relationship of these variables to transition to chronic are unclear, group x obesity interactions are not expected.
- 9.1.14 Outcomes for this aim will utilize the same measures and sources as PA1-2, SA3 but will also include EMR data on patient co-morbidities, smoking status, and socioeconomic status.
- 9.1.15 **Missing data:** Baseline characteristics, such as age, gender, and health insurance status, will be compared between patients with complete assessment data to those with missing data by treatment group in order to assess potential biases that may exist in the complete case analysis. Sensitivity analyses for the primary and secondary outcomes will be conducted using several methods, which have different missing data assumptions.
- 1) Complete case analyses, which assumes missing data are completely at random,
  - 2) Multiple imputation using M=10 imputations, which assumes missing at random, and
  - 3) Assigning poor scores and good scores for missing values differentially by treatment group, which aligns with non-ignorable missingness (the data missingness is nonrandom and related to the actual value).

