## 9.5 Data analyses

- 9.5.1 **Primary outcome 1:** This initial analysis (**PA1**) will use a generalized linear mixed model with a logit link controlling for block set (see Randomization) and a fixed effect for intervention accounting for the cluster RCT design with a random clinic effect. Primary analyses will also adjust for patient characteristics (maladaptive pain coping behaviors such as catastrophizing and fear avoidance, functional impairment as measured by the Oswestry, and presence

of psychiatric comorbidities), as these have been associated with higher transition to chronic LBP. The intraclass correlation coefficients will also be estimated and reported for all outcome measures to assess the assumptions for sample size analyses and also for future investigations using similar designs and outcomes. Analysis for the secondary aims (**SA4** and **SA5**) will be largely descriptive assessing the proportion of patients who transition to chronic LBP among the low and moderate risk observational cohort. The proportion and confidence interval will be estimated using generalized linear models adjusting for clustering.

- 9.5.2 **Primary outcome 2:** This aim (**PA1**) will be analyzed using contrasts from a linear mixed models analysis for 6-month back-related function (Oswestry) controlling for baseline Oswestry and the block set (see Randomization). The intervention will first be explored by time interaction, and then proceed to a main effects model with only group and time. For the secondary aims (**SA4** and **SA5**) patient-centered outcomes, such as functional status, would use general linear models if deemed appropriate based on normality assumptions. If normality is hugely violated, a cutpoint for 'response' will be applied.

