## 17 Appendix 3: Oswestry LBP Questionnaire

| Oswestry LBP Questionnaire  |   |
|--|---|
| 
This questionnaire is designed to give us information as to how your back (or leg) trouble affects your ability to manage in everyday life. Please answer every section. Mark one box only in each section that most closely describes you today.
   |   |

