| 
Section 1 – Pain Intensity
 
 I have no pain at the moment.
 
 The pain is very mild at the moment.
 
 The pain is moderate at the moment.
 
 The pain is fairly severe at the moment.
 
 The pain is very severe at the moment.
 
 The pain is the worst imaginable at the moment.
 
Section 2 – Personal Care (washing, dressing, etc.)
 
 I can look after myself normally without causing additional pain.
 
 I can look after myself normally but it is very painful.
 
 It is painful to look after myself and I am slow and careful.
 
 I need some help but manage most of my personal care.
 
 I need help every day in most aspects of self care.
 
 I do not get dressed, I wash with difficulty and stay in bed.
 
Section 3 – Lifting
 
 I can lift heavy weights without additional pain.
 
 I can lift heavy weights but it gives additional pain.
 
 Pain prevents me from lifting heavy weights off the floor but I can manage if they are conveniently positioned, e.g. on a table.
 
 Pain prevents me from lifting heavy weights but I can manage light to medium weights if they are conveniently positioned.
 
 I can only lift very light weights.
 
 I cannot lift or carry anything at all.
 
Section 4 – Walking
 
 Pain does not prevent me from walking any distance.
 
 Pain prevents me from walking more than one mile.
 
 Pain prevents me from walking more than a quarter of a mile.
 
 Pain prevents me from walking more than 100 yards.
 
 I can only walk using a cane or crutches.
 
 I am in bed most of the time and have to crawl to the toilet.
 
Section 5 – Sitting
 
 I can sit in any chair as long as I like.
 
 I can sit in my favorite chair as long as I like.
 
 Pain prevents me from sitting for more than 1 hour.
 
 Pain prevents me from sitting for more than half an hour.
 
 Pain prevents me from sitting for more than 10 minutes.
 
 Pain prevents me from sitting at all.
 | 
Section 6 – Standing
 
 I can stand as long as I want without additional pain.
 
 I can stand as long as I want but it gives me additional pain.
 
 Pain prevents me from standing for more than 1 hour.
 
 Pain prevents me from standing for more than half an hour.
 
 Pain prevents me from standing for more than 10 minutes.
 
 Pain prevents me from standing at all.
 
Section 7 – Sleeping
 
 My sleep is never interrupted by pain.
 
 My sleep is occasionally interrupted by pain.
 
 Because of pain I have less than 6 hours sleep.
 
 Because of pain I have less than 4 hours sleep.
 
 Because of pain I have less than 2 hours sleep.
 
 Pain prevents me from sleeping at all.
 
Section 8 – Sex Life (if applicable)
 
 My sex life is normal and causes no additional pain.
 
 My sex life is normal but causes some additional pain.
 
 My sex life is nearly normal but is very painful.
 
 My sex life is severely restricted by pain.
 
 My sex life is nearly non-existent because of pain.
 
 Pain prevents me from having any sex life at all.
 
Section 9 – Social Life
 
 My social life is normal and causes me no additional pain.
 
 My social life is normal but increases the degree of pain.
 
 Pain has no significant effect on my social life apart from limiting my more energetic interests, e.g., sport, etc.
 
 Pain has restricted my social life and I do not go out as often.
 
 Pain has restricted my social life to home.
 
 I have no social life because of pain.
 
Section 10 – Traveling
 
 I can travel anywhere without pain.
 
 I can travel anywhere but it gives me additional pain.
 
 Pain is bad but I am able to manage trips over two hours.
 
 Pain restricts me to trips of less than one hour.
 
 Pain restricts me to short necessary trips of under 30 minutes.
 
 Pain prevents me from traveling except to receive treatment.
 |

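### Does the Oswestry score need a written rule for forms on which the sex-life section is left blank?

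*Combined protocol and SAP*

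**What the plan says.** Section 3.3.2 gives the only scoring rule. Each area is scored 0 to 5, and the ten areas "are added together, resulting in a maximum score of 50. This score is doubled and interpreted as a percentage of patient-perceived disability". The same paragraph lists the areas as including "sex life (if applicable), social life, and ability to travel". The form in Appendix 3 puts the same qualifier on its Section 8, offers six scored statements there, and has no box for a patient to whom the section does not apply. Its general instruction is "Please answer every section. Mark one box only in each section that most closely describes you today".

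The score is used twice in Section 9.5. The PA2 model takes the 6-month Oswestry as outcome, "controlling for baseline Oswestry and the block set". The PA1 model adjusts for, among other things, "functional impairment as measured by the Oswestry".

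Section 9.1.15 plans three approaches to missing data. The first is "Complete case analyses, which assumes missing data are completely at random"; the others are multiple imputation with ten imputations, and assigning poor and good scores differentially by arm. It does not say whether a form with one blank area counts as missing, or whether items or totals are imputed.

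**The concern.** The plan expects that one area will not apply to some patients, yet its rule fits only ten answers. Three treatments of a nine-answer form are open:

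- double whatever sum is there, so that the blank counts as zero;
- treat the whole score as missing;
- rescale to the answered areas, or impute the missing item.

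The first lowers the scores of the patients concerned. It could also produce an apparent improvement in a patient who answers the section at baseline and skips it at 6 months. The second discards nearly complete forms. If the baseline form is the incomplete one, it also removes from a complete-case PA1 model a patient whose chronic-pain status at 6 months is known. A blank that arises because the section does not apply is unlikely to be missing completely at random. For a primary outcome, one would not want the choice left until the data are in hand.

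**Working it through.** **Inputs.** Ten areas scored 0–5 (3.3.2); 1,860 enrolled, 40% non-response, coefficient of variation of cluster size 0.65 (9.2.2); 60 clinics and ICC 0.05 (9.2.3). The ICC is stated for PA1 and is assumed here for PA2. The share *s* of forms with Section 8 blank is not in the documents and is assumed throughout.

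**The plan's own figure.** 10 × 5 = 50, and 50 × 2 = 100. Doubling is therefore 100/50, the conversion of a sum to a percentage of its maximum. With nine answers the maximum is 9 × 5 = 45, and the same conversion is 100 × sum/45.

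**Literal doubling of a nine-answer form.** 2 × sum divided by (100 × sum/45) = 90/100 = 0.90 at every level.

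| Sum of nine | Doubled | Rescaled | Gap |
|---|---|---|---|
| 9 | 18 | 20 | 2 |
| 18 | 36 | 40 | 4 |
| 27 | 54 | 60 | 6 |
| 45 | 90 | 100 | 10 |

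A patient with the same answer in every area at both visits who skips Section 8 only at 6 months would show a false improvement of 2 to 10 points at true scores of 20 to 100.

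**Effect on means and on the arm difference.** If a share *s* is scored at 0.90, the group mean is multiplied by 1 − 0.10*s*, taking skippers to be like the others on average. At an assumed mean of 40 the shift is 0.10 × 40 × *s*: 0.2 points at *s* = 5% and 1.2 points at 30%. With the same *s* in both arms, the arm difference is multiplied by the same factor: 0.995 at 5% and 0.970 at 30%. If blanks differed between arms by an assumed 5 to 20 percentage points, the difference at a mean of 40 would move by 0.10 × 40 × 0.05 = 0.2 to 0.10 × 40 × 0.20 = 0.8 points.

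**Discarding the form.** Expected completers are 1,860 × 0.60 = 1,116, or 1,116/60 = 18.6 per clinic. The variance of the arm difference is proportional to [1 + ((1 + 0.65²)m − 1) × 0.05]/m, where m is the number analysed per clinic. If the same patients skip at both visits, m = 18.6(1 − *s*).

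| *s* (assumed) | Lost | m | Standard error ratio |
|---|---|---|---|
| 5% | 56 | 17.67 | 1.011 |
| 10% | 112 | 16.74 | 1.023 |
| 20% | 223 | 14.88 | 1.051 |

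If skipping were independent at the two visits, m = 18.6(1 − *s*)². The loss would then be 109 patients at 5% and 402 at 20%, with ratios of 1.022 and 1.111. That is a poor model for a section skipped because it does not apply, since this should mostly persist over six months.

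**Scale.** Planned non-response already removes 1,860 − 1,116 = 744 patients.

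**The case for a change.** The best argument for a change is that this is a primary outcome, a sentence would settle it, and the choice might be hard to recover later. Baseline forms come by portal, tablet or paper through five health systems' EMRs, and the 6-month forms by telephone, e-mail or post (10.1). Skipping and scoring could therefore differ by site and by visit. If only totals were extracted, rescaling afterwards would be impossible, and Appendix 6 names no Oswestry items.

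Part of this stands. The rule is unwritten, and 9.1.15 does not supply it. An individual's change score could be off by several points under literal doubling.

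The rest carries less weight:

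- Clinics are randomized within each study site (3.2), and both models control for block set. A site-wide difference in how forms are built or scored therefore falls on both arms alike. A shift at 6 months common to both arms also drops out of the PA2 contrast.
- Follow-up assessors are blinded (9.2.1), and the same questionnaires are used in both arms (Table 1).
- Appendix 6 lists no questionnaire at all, so its silence on Oswestry items says little. Section 4.3.3 has every EMR modified to accept the ten-item form, and Section 12 gives data dictionaries and extraction templates to the Data Integrity Committee. No passage says item-level storage outright, but these point that way.
- The general instruction on the form and the qualifier on Section 8 read naturally as a rule and its exception.

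A formal threshold has its own cost. Requiring nine answered sections would discard a patient to whom Section 8 does not apply and who misses one other section, while a patient to whom it does apply may miss one freely.

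**Conclusion.** The gap is real, but it is a missing scoring detail that analysts fill sensibly. Since 3.3.2 reads the score as a percentage, dividing by the maximum of the answered sections follows directly, and item-level imputation under 9.1.15 is also open. Neither contradicts anything written.

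The least favourable handling would cost little. Literal doubling leaves at least 97% of the arm difference at up to 30% blanks. Discarding forms adds at most about 5% to the standard error at up to 20% blanks in the same patients, and imputation is already planned. No bias between arms is shown.

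This rests on assumed blank rates that are similar in the two arms, on skippers resembling other patients on average, and on the PA1 intraclass correlation holding for the Oswestry. The conclusion would weaken if blanks were both common and clearly different between arms, and nothing in the documents suggests that. The plan can stand as written.

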### 3.4 Study population and sites

The target population for this study will be adult patients who present to primary care physicians (i.e., internal medicine, family practice, and geriatric medicine physicians) with a primary complaint of LBP. Patients will be recruited from health systems in five regional areas that surround: 1) Pittsburgh, PA (UPMC); 2) Boston, MA (Boston Medical Center); 3) Baltimore, MD (Johns Hopkins Medicine); 4) Charleston, SC (Medical University of South Carolina); and 5) Salt Lake City, UT (Intermountain Healthcare). Within the individual regional areas, primary care clinics have been identified that represent community-based PCP clinics. In all instances, there are more potential sites than are required for successful completion of the trial, which will allow flexibility in the randomization scheme and alternatives should there be individual PCP-clinic recruitment shortfalls. This large, nation-wide group of clinics across five different health systems provides a high level of pragmatism for the PRECIS-2 organizational domain because the systems will be variable with regards to provider expertise, resources, and organizational structure.

Certain patient subgroups are of particular interest (**SA5**) given greater risk for poorer LBP outcomes as demonstrated in observational cohort studies. Adequate enrollment will be assured to have statistical power to conduct subgroup analyses of patients with lower socioeconomic status (using insurance as a proxy) and the comorbid conditions of smoking, depression, and obesity. Identification of subgroups will be based on information obtainable in the EMR. The participating primary care clinics will be sampled to reflect gender, race, and ethnicity proportions of the population being served at the recruitment sites.

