## 9.2 Randomization, sample size and power – RCT cohort

- 9.2.1 **Randomization** will occur at the clinic level, which was chosen for the pragmatic reason that randomizing patients within a clinic would result in cross contamination of the interventions within the same clinic. The biostatisticians and the individuals conducting the 6-month assessments will be blinded to the randomization assignment to avoid bias in analyses and data capture.
- 9.2.2 **Sample size** is based on the first primary outcome of the transition rate to chronic LBP at month 6. We propose to enroll N=1860 high risk acute LBP patients. We are targeting an average of n=31 enrolled high risk patients per clinic ( $60 \times 31 = 1860$ ) to account for the variation in cluster sizes (assuming coefficient of variation=0.65) and 40% non-response rate at 6 months.
- 9.2.3 **Power:** With a total of 60 PCP clinics for randomization, m=30 clinics per intervention strategy and fixed n=10-14 completers per clinic for the 6-month assessment, we will have just over 80% power to detect a 40% reduction in transition to chronic LBP assuming the control arm has a transition rate of 25%-30% and the intraclass correlation is 0.05, which is an upper bound for what has been observed in other cluster randomized trials with respect to either pain or LBP. Assuming that low and medium risk subjects with acute LBP have an expected 20% transition to chronic and using data on obesity and smoking rates based on national surveys, depression rates based on prevalence rates reported in primary care, and proportions of underserved patients estimated from patient registries at each of the five regional sites, the planned sample size for the observational cohort is sufficient to detect at least a 30% relative difference (6% absolute difference) from 20% with powers ranging from 79% to 87%. The study would have 65% power to detect a 40% relative or 8% absolute difference (hypothesized increased rate of transition) for the depression subgroup.

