- 9.2.4 **Treatment assignment procedures:** Detecting an interaction effect the same size as the overall intervention effect would require a four-fold increase in the effective sample size (more clinics and patients accounting for clustering), which is not feasible. There will be sufficient power to detect stronger intervention effects in some *a priori* defined subgroups at the participant level (smoking, depression, obesity, lower SES) if the cohort is evenly split.
- 9.2.5 **Analysis of randomization:** Distributions of baseline characteristics for clinics and patients will be compared between the study arms to assess effectiveness of the randomization, and statistical or clinical differences will be adjusted for in sensitivity analyses. All analyses for treatment group comparisons will use an intention-to-treat approach and results will be reported using the CONSORT extension to cluster randomized trials. This approach is highly pragmatic per the PRECIS-2 primary analysis domain.

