|-----------------------------|---|---|---|---|
| Underserved (n=665 of 2464) | 74  | 87  | 95  | 98  |
| Obesity (n=640 of 2464)     | 73  | 86  | 94  | 98  |
| Depression (n=184 of 2464)  | 33  | 44  | 54  | 65  |
| Smoking (n=493 of 2464)     | 64  | 79  | 89  | 95  |

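### Section 3.4 assures subgroup power that section 9 does not support for depression or for planned-size effects in the RCT cohort, and 9.5.1-9.5.2 do not write out the subgroup arm comparison that H5 needs

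*Combined protocol and SAP*

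**What the plan says.** **Power.** Section 3.4 says "Adequate enrollment will be assured to have statistical power to conduct subgroup analyses of patients with lower socioeconomic status" and adds smoking, depression and obesity. It names no cohort, effect size or power level.

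Section 9 is more guarded:

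- In Table 3 (section 9.3.3), the row "Depression (n=184 of 2464" shows 33, 44, 54 and 65% for differences of 5, 6, 7 and 8 points from a 20% transition rate. The prose repeats the last figure in 9.2.3 and 9.3.3: "The study would have 65% power to detect a 40% relative or 8% absolute difference" for depression. The underserved, obesity and smoking rows show 79-87% at 6 points.
- For the RCT cohort, 9.2.4 says "Detecting an interaction effect the same size as the overall intervention effect would require a four-fold increase in the effective sample size", and calls that infeasible. It then says "There will be sufficient power to detect stronger intervention effects in some" of the predefined subgroups, on the condition "if the cohort is evenly split".

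**Analysis.** SA5 belongs to the RCT cohort (3.1.1, 9.1.12) and to the observational cohort (1.2.4, 3.1.2). H5 (1.2.5, 9.1.13) predicts that GBC+PIPT beats GBC in patients with depression or low socioeconomic status. Sections 9.4.1 and 9.4.2 extend the comparison of intervention with comparator clinics to the SA5 subgroups for both primary outcomes. For transition, 9.5.1 describes the SA5 analysis as mostly descriptive, estimating proportions in the low- and moderate-risk cohort; 9.3.1 says those patients do not receive PIPT. For function, 9.5.2 gives SA5 general linear models with no arm or clinic term stated. For utilization, 9.5.3 refers SA5 back to the mixed models used for SA3.

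**The concern.** There are two separate problems.

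First, someone who reads only 3.4 learns that all four subgroups are adequately powered. Depression is the weakest of the four in Table 3, and it is also one of the two subgroups in which H5 expects a benefit. A null depression result could then be read as evidence of no difference when the design had little chance of showing one.

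Second, H5 is a between-arm hypothesis. The analysis that 9.5.1 describes for SA5 sits in a cohort where the arms do not differ by PIPT, so followed as written it cannot test H5 for transition. For function, the model is left open enough that the arm comparison would have to be specified later, possibly after the data are seen.

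**Working it through.** **1. Reproducing Table 3.** Inputs from 9.3.3 and Table 3: 6,900 enrolled, 60% response, 60 clinics, ICC 0.01, reference rate 20%, two-sided 0.05.

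- Completers: 6,900 × 0.60 = 4,140, or 69 per clinic.
- Design effect: 1 + (69 − 1) × 0.01 = 1.68.
- Effective N: 4,140 / 1.68 = 2,464, as stated.
- Power = Φ(d / SE − 1.96), with SE = √[p₁(1−p₁)/n + 0.20 × 0.80/(2,464 − n)] and p₁ = 0.20 + d (unpooled variance, subgroup against the remainder).
- Depression at 8 points: SE = √(0.28 × 0.72/184 + 0.16/2,280) = 0.0341; 0.08/0.0341 = 2.34; Φ(2.34 − 1.96) = 64.9%.
- Whole depression row: 32.8, 43.5, 54.5, 64.9% (stated 33, 44, 54, 65).

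All 16 cells reproduce within 1 point, so Table 3 stands.

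**2. What 80% would need for depression.** Same formula:

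- With n = 184, 80% is reached at about 9.7 points (a relative difference of 49%).
- At 8 points it needs about 272 effective patients, 11% of 2,464 instead of 7.5%.

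**3. RCT cohort, subgroup of exactly half.** Inputs from 9.2.2-9.2.3: 30 clinics per arm, ICC 0.05, 40% reduction from 25% (to 15%) or from 30% (to 18%). Assumed: unpooled two-sided Z-test at 0.05. Two descriptions of cluster size are given: "fixed n=10-14 completers per clinic for the 6-month assessment" in 9.2.3, and in 9.2.2 an average of 31 enrolled "to account for the variation in cluster sizes (assuming coefficient of variation=0.65) and 40% non-response rate at 6 months", that is 31 × 0.6 = 18.6 completers with CV 0.65.

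For m completers per clinic in the analysis set, the design effect is DE = 1 + (m − 1) × 0.05 for fixed clusters, or DE = 1 + [(1 + 0.65²)m − 1] × 0.05 with CV 0.65. Effective n per arm is 30m/DE. The half-cohort subgroup uses half of m.

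| Inputs | Whole-trial power | Subgroup DE | Effective n per arm | Subgroup power |
|---|---|---|---|---|
| 14 fixed, 25% control | 81.1% | 1.30 | 161.5 | 62.0% |
| 10 fixed, 30% control | 82.3% | 1.20 | 125.0 | 61.2% |
| 18.6, CV 0.65, 25% control | 79.7% | 1.61 | 173.1 | 65.0% |
| 18.6, CV 0.65, 30% control | 88.2% | 1.61 | 173.1 | 75.2% |

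The first two rows are the fixed-size pairings that match the overall power stated in 9.2.3, slightly above 80%. The last two use the enrolment inputs of 9.2.2. Together they give about 61-75% for the planned 40% reduction. In the same four rows, 80% subgroup power would need a reduction of about 42-49%, which indicates how strong a stronger effect in 9.2.4 would have to be.

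The documents give no subgroup shares for high-risk patients, so I give no RCT figure for any named subgroup. The Table 3 shares (184/2,464 = 7.5% up to 665/2,464 = 27%) belong to the other cohort, but they show that an even split is not a given.

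**4. Analysis text side by side.**

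| Outcome | Comparison called for in SA5 | Analysis written for SA5 |
|---|---|---|
| Transition | By arm (H5, 9.4.1) | Proportions in the low/moderate-risk cohort (9.5.1) |
| Function | By arm (H5, 9.4.2) | General linear model, no arm or clinic term stated (9.5.2) |
| Utilization | By arm (H5, 9.4.3) | As for SA3, mixed model with clinic effects (9.5.3) |

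Only the third row joins up.

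**The case against.** The strongest reply is that section 9 hides nothing. The 65% for depression appears twice in prose and once in Table 3, and 9.2.4 openly limits what the RCT subgroups can show. Section 3.4 is a narrative on population and sites, no sample size depends on it, and 80% is not a stated subgroup target. All of that is true, and it is why the severity is modest. It does not make the sentence in 3.4 correct: 33-65% is not assured power, and the two places should agree.

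On the analysis, one can say that 9.4.1-9.4.2 already prescribe the arm comparison and that using the primary models within subgroups is the evident intent. I think that is the likely intent. But 9.5.1 points SA5 to a different cohort, so the intent needs to be written down.

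Three stronger readings are tempting and are not supported:

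- *Even-split power as low as 51%.* This pairs 10 completers per clinic with a 25% control rate. Whole-trial power there is only 72.7%, which does not match the overall power claimed in 9.2.3.
- *Clinic clustering would be ignored for function, inflating type I error.* Section 9.5.2 names no arm test for SA5 and the documents give no ICC for the Oswestry, so any such figure is hypothetical. Sections 3.2, 9.2.5, 9.5.1 and 9.5.3 all point to accounting for clinics. The gap is an unstated term.
- *The power calculation for the subgroups is wrong.* It is not; Table 3 reproduces.

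**Conclusion.** The point holds as an internal inconsistency of modest severity.

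- The assurance in 3.4 is contradicted for depression by Table 3 (33-65% across the tabulated differences). In the RCT cohort it is broader than 9.2.4, where an even split gives about 61-75% power for the planned effect. For the underserved, obesity and smoking subgroups of the low/medium-risk cohort, Table 3 does support it at differences of about 6 points.
- The subgroup arm comparison required by H5 is not written for either primary outcome. Utilization is covered by 9.5.3.

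The depression figures rest on the document's own inputs. The RCT range also assumes an unpooled Z-test and a subgroup that is half of every clinic's completers. The 80% level is used only for reference.

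**What to change.** (a) In 3.4, replace the assurance with a qualified statement that refers to Table 3 and 9.2.4 and says that power is limited for depression and, in the RCT cohort, for effects of the planned size. Table 3 and 9.2.4 can stay as they are.

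(b) In 9.5.1 and 9.5.2, state that H5 is assessed in the high-risk RCT cohort with the primary mixed models (random clinic effect, block set) plus subgroup and arm-by-subgroup terms. Report the arm effect within each subgroup and the interaction, each with a confidence interval, and note the low precision that 9.2.4 already concedes. Keep the observational-cohort proportions as a separate descriptive item.

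The cost is a less favourable power statement and a little more analysis. No additional patients are needed.
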